Study Number: NCT02018562

Official Title: *Evaluation of a Tracheostomy Tube That Enables Communication*

Principal Investigator: [name]

Date: 12/19/2013

JHM IRB - eForm A – Protocol

Use the section headings to write the JHM IRB eForm A, inserting the appropriate material in each. If a section is not applicable, leave heading in and insert N/A.

- **When submitting JHM IRB eForm A (new or revised), enter the date submitted to the field at the top of JHM IRB eForm A.**

1. Abstract

- a. Provide no more than a one page research abstract briefly stating the problem, the research hypothesis, and the importance of the research.

Verbal communication greatly affects people’s autonomy and is directly related to how they perceive their quality of life (Hess, 2005). The need for effective communication is heightened during critical illness. Critically ill patients requiring mechanical ventilation often need an endotracheal tube or a tracheostomy tube. When a patient is intubated, communication is often accomplished through facial expressions, gestures, and/or writing, depending on the person’s neurological status and sedation level (Batty, 2009). However, these simple modes of communication are not always effective and can often result in frustration for the patient (Patak et al., 2006).

A benefit of tracheostomy over an endotracheal tube is that it may facilitate the ability to communicate by mouthing words. Additionally, when a person receives a tracheostomy tube, several methods used to elicit phonation can be utilized, including the use of a one-way speaking valve, leak speech, and digital occlusion. All of these methods require toleration of cuff deflation (Batty, 2009; Astrachan, Kirchner, & Goodwin, Jr., 1988; Hess, 2005; Nomori, 2004). Unfortunately, some critically ill mechanically ventilated patients cannot tolerate cuff deflation despite their ability to maintain arousal and to initiate meaningful communication. Uniquely designed tracheostomy tubes are available that enable speech and do not require cuff deflation. These “talking tracheostomy tubes” are rarely used because of a general lack of awareness among care providers. However, recently, at the Johns Hopkins Hospital, there has been an increase in the use of these tubes to facilitate speech. One of the tubes that has proven to be effective is the Blueline Ultra Suctionaid (BLUSA).

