In 2010, we conducted a retrospective review of 4 cases and found that BLUSA tracheostomy helped facilitate communication in this unique population (IRB #: NA_00041547). Now, we would like to formally conduct a prospective study to evaluate the outcomes of patients using a BLUSA using a pretest-posttest research design.

Identifying the predictors of intelligibility and the impact of BLUSA on Quality of Life (QOL) and communication will promote communication between patients and healthcare providers. This empowers patients and allows healthcare staff to obtain a more accurate assessment of patients’ condition and tailor care accordingly.

2. Objectives (include all primary and secondary objectives)

Specific Aim 1: Determine the impact of a BLUSA on QOL in patients requiring prolonged mechanical ventilation in the hospital

Hypothesis 1a: The mean health-related QOL scores of patients who use BLUSA will be significantly higher compared to patients who do not use BLUSA.

Hypothesis 1b: The mean voice-related QOL scores of patients who use BLUSA will be significantly higher compared to patients who do not use BLUSA.

Specific Aim 2: Determine the outcomes of communication following the use of BLUSA in patients requiring prolonged mechanical ventilation in the hospital.

Hypothesis 2: Effectiveness of communication in patients who use BLUSA will be significantly improved compared to patients who do not use BLUSA.

Research Question 2a: What is the time to speech among patients who are unable to speak using a speaking valve?

Research Question 2b: What is the frequency and duration of speech with use of BLUSA?

Specific Aim 3: Identify the predictors of intelligibility in patients requiring prolonged mechanical ventilation in the hospital.

Hypothesis 3: Several factors such as age, sex, educational level, primary diagnosis, indications for mechanical ventilation, indication for tracheostomy, co-morbidities, and severity of illness will significantly contribute to speech intelligibility in patients requiring prolonged mechanical ventilation in the hospital.

Specific Aim 4: Validate the speech item in the health-related QOL instrument to evaluate speech as a domain of QOL in patients requiring prolonged mechanical ventilation in the hospital

Hypothesis 4: The mean health-related QOL scores will moderately correlate negatively with mean voice-related QOL (VR-QOL) questionnaire (criterion validity).

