- d. Justification of why participants will not receive routine care or will have current therapy stopped.
If patient is not willing to participate in the study, their routine care will not be altered. They will still have the opportunity to use BLUSA per current standard of care. Patients who are in the control group will also receive BLUSA but a week late.
- e. Justification for inclusion of a placebo or non-treatment group. N/A
- f. Definition of treatment failure or participant removal criteria.
If there is a change in clinical condition that prevents study team from continuing with the BLUSA trial or if the patient is discharged from the hospital, the patient will be dropped from the study.
- g. Description of what happens to participants receiving therapy when study ends or if a participant's participation in the study ends prematurely.
If participants receiving BLUSA complete the study (after the post-assessment), they will continue to use BLUSA per our current standard of care. If the participant's participation using BLUSA ends prematurely due to change in clinical condition, then they will be dropped from the study. But if their condition improves and warrants reuse of BLUSA, they will be offered BLUSA per our standards of care but will not be re-enrolled in the study.

5. Inclusion/Exclusion Criteria

Inclusion Criteria:

Mechanically ventilated via tracheostomy
Awake, alert, and attempting to communicate
Able to understand English

Exclusion Criteria:

Delirium
Fresh tracheostomy within 48 hours
Laryngectomy

6. Drugs/ Substances/ Devices

- a. The rationale for choosing the device to be used.
 - 1. Enables speech in patients who are mechanically ventilated and unable to tolerate cuff deflation.
 - 2. Over the last couple of years, the use of BLUSA has increased dramatically at the Johns Hopkins Hospital.
 - 3. Its impact on quality of life is unknown.
 - 4. This device has the speech attachment that the routine tracheostomy tubes do not have.
 - 5. This device' speech attachment has a wider lumen and is detachable for cleaning.
- b. Justification and safety information if FDA approved drugs will be administered for non-FDA approved indications or if doses or routes of administration or participant populations are changed. N/A
- c. Justification and safety information if non-FDA approved drugs without an IND will be administered. N/A

7. Study Statistics

- a) Primary outcome variables
 1. Quality of life
- b) Secondary outcome variables

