 1. Sentence intelligibility
 2. Level of independence with BLUSA
 3. Patient satisfaction with BLUSA
- c) Variables of Interest
 1. Age, Sex, Race
 2. Indication for ICU admission
 3. Indication for Tracheostomy
 4. Severity of Illness (measured by SOFA scores)
 5. Delirium (CAM-ICU)
 6. Sedation (RASS)
 7. Motor Speech (Cranial nerve assessment V, VII, IX, X, and XII)
 8. Information about secretions (suction frequency, secretion quality and quantity)
 9. Time to SLP consult in days
 10. Time to initial in-line speaking valve trial
 11. Severity of Illness
 12. Time to BLUSA in days
 13. Time between speaking valve trial and BLUSA

d) Statistical plan including sample size justification and interim data analysis.

In order to compare changes in health-related quality of life from pre-assessment to post-assessment, we need 73 participants in each group. This allows for a 20% drop out rate and is based on a sample size of 61 individuals in each group to achieve 80% power and a clinically meaningful 20% increase in health-related QOL mean score from 61.16 (SD \pm 21.74) to 73.38 (SD \pm 26.09) based on another "Quality of Life in Mechanically Ventilated Patients" study by PI. We assume a two-tailed test with a significance level of $\alpha = 0.05$.

Interim data analysis will be conducted after 12 months of data collection. Mean, standard deviation, median and inter-quartile range will be calculated for continuous variables. Paired t-tests will be used to compare pre and post assessment scores for continuous variables. Frequencies and percentages will be calculated for categorical variables. Chi square and Fisher Exact tests will be used to compare pre and post assessment scores of categorical variables. Validation of the QOL instrument will include calculation of Cronbach's alpha, Pearson correlation, Kappa.

e) Early stopping rules.

Reasons for stopping data collection for a participant will include

1. change in clinical condition
2. discharge from the hospital

8. Risks

a. Medical risks, listing all procedures, their major and minor risks and expected frequency.

Administration of questionnaires repeatedly can be burdensome. In addition, questions about their quality of life while mechanically ventilated may be emotionally distressing.

b. Steps taken to minimize the risks.

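### Section 5 does not require that patients be unable to speak by ordinary means, and the listed data would not show who is, although the rationale and Research Question 2a concern exactly those patients

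*Combined protocol and SAP*

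**What the plan says.** **Eligibility (section 5).** The three inclusion criteria are "Mechanically ventilated via tracheostomy", "Awake, alert, and attempting to communicate" and "Able to understand English". The three exclusions are delirium, laryngectomy and "Fresh tracheostomy within 48 hours". None refers to cuff deflation, a speaking-valve trial or present ability to speak.

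**Intended users.** The abstract (section 1) explains that valves, leak speech and digital occlusion all depend on a deflated cuff, and that "some critically ill mechanically ventilated patients cannot tolerate cuff deflation". It presents talking tubes as the option for that group. The first reason for choosing the device (section 6a) is "Enables speech in patients who are mechanically ventilated and unable to tolerate cuff deflation". Research Question 2a (section 2) asks "What is the time to speech among patients who are unable to speak using a speaking valve".

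**Aims (section 2).** Aims 1 to 4 name a wider group: hospital patients on prolonged mechanical ventilation. Hypotheses 1a, 1b and 2 compare BLUSA users with non-users and set no condition on cuff or valve status.

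**Data.** The itemised variables (sections 4a and 7c) include time to the first in-line valve trial and "Time between speaking valve trial and BLUSA". Both are timings. Neither the result of the valve trial nor cuff tolerance is listed.

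**Sample size (section 7d).** The plan needs 61 evaluable per group for 80% power, two-sided 0.05, to detect a rise in mean QOL from 61.16 (SD 21.74) to 73.38 (SD 26.09).

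**The concern.** The rationale describes a device for people who have no other route to speech, but the entry criteria do not separate them from people who do. Two consequences follow.

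The first holds whatever the numbers are. Research Question 2a is defined on patients who failed a valve, and the listed data cannot pick them out. Its denominator is therefore undefined at analysis.

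The second is conditional. If BLUSA improves quality of life mainly by giving speech to those without it, patients who already speak will gain less. A control patient who speaks with a valve during the waiting week is also a different comparator from one who cannot speak at all. The mean between-group difference would then be smaller than in the intended users, and the sample size has no reserve to absorb that.

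**Working it through.** **1. Passages side by side.**

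| Place | Population |
|---|---|
| Section 5 | Any awake, communicating, English-understanding patient ventilated via tracheostomy, with three exclusions |
| Section 2, Aims 1–4 | Hospital patients on prolonged ventilation |
| Section 1 and section 6a | Unable to tolerate cuff deflation |
| Section 2, Research Question 2a | Unable to speak with a valve |
| Sections 4a and 7c, data | Valve-trial timing only |

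On cuff and valve status, section 5 agrees with the Aims. It does not agree with the rationale or Research Question 2a, and the data list does not bridge the two.

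**2. Reproducing the plan's figure.** Inputs from section 7d: difference 73.38 − 61.16 = 12.22; SDs 21.74 and 26.09; two-sided alpha 0.05; power 80%.

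- Common SD = √((21.74² + 26.09²)/2) = 24.01.
- n per group = 2 × [24.01 × (1.960 + 0.842)/12.22]² = 60.6, so 61. The stated figure reproduces.
- At n = 61 the standard error is 24.01 × √(2/61) = 4.35. Power = Φ(12.22/4.35 − 1.96) = 80.2%. A t-based calculation gives 79.6%.

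**3. Illustration of dilution.** The documents give no share of already-speaking patients and no effect in them. Assume that 12.22 is the effect in the intended users, that a share f gains nothing, and that the SDs are unchanged. The expected difference is 12.22 × (1 − f), and power = Φ(12.22(1 − f)/4.35 − 1.96).

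| f (assumed) | Difference | Power at 61 per group, normal (t-based) | Evaluable n per group for 80% |
|---|---|---|---|
| 0 | 12.22 | 80.2% (79.6%) | 61 |
| 10% | 11.00 | 71.5% (70.8%) | 75 |
| 20% | 9.78 | 61.3% (60.6%) | 95 |
| 30% | 8.55 | 50.3% (49.6%) | 124 |
| 40% | 7.33 | 39.2% (38.7%) | 169 |

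Letting the intervention-group SD reflect the mixture of gainers and non-gainers changes little: at f = 20%, power is 62.0% and n is 94.

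**4. Sensitivity to zero gain.** If already-speaking patients gain half the effect, f = 20% gives 12.22 × (1 − 0.10) = 11.00 points, which is the 10% row: about 71%, not 61%.

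**5. What the subset could show.** At f = 20%, the unable-to-speak subset would be about 61 × 0.80 = 49 per group. If the full 12.22 points applies there, the standard error is 24.01 × √(2/49) = 4.85 and power is Φ(12.22/4.85 − 1.96), about 71%. That is below the planned 80% but above the 61% for the diluted comparison at the same f.

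**The case against.** The strongest reply is that section 5 matches the Aims. A reader might infer that the enrolled population is not the one the hypotheses address, but the documents do not support that. The Aims name prolonged-ventilation patients generally, and the powered comparison is users against non-users. Only Research Question 2a is narrower, and it is descriptive. Nor do the documents say that controls must be unable to speak. This objection stands.

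A reader might also infer that the trial is underpowered by a known amount. That is not supported either. The 12.22 points is a 20% rise, judged clinically meaningful, applied to a mean from an earlier study of ventilated patients. Nothing ties it to cuff-intolerant patients. If it was meant as a target for the broad population, there is nothing to dilute. The 4 of 74 ventilated patients who received a talking tube in 2010 (section 3) do not estimate f, because the ability of the other 70 to speak is not reported.

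Practice may also select valve failures. Placement needs a prescriber's order, controls receive BLUSA as standard care, and recording an interval from valve trial to BLUSA suggests that a valve trial usually comes first. The flow chart in section 4 is not visible in the text available and could contain such a step. So f may be small, but no visible text makes valve failure an entry condition.

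Finally, narrowing entry could slow accrual against a target of 2 × 73 = 146, by an amount the documents do not allow one to estimate.

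What remains is the mismatch between section 5 and the rationale, and the missing valve result. The pilot label in section 4a does not remove either, since section 7d states a powered two-sided comparison.

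**Conclusion.** The point holds in limited form. Section 5 can admit patients who already speak with a valve. The abstract, section 6a and Research Question 2a concern those who cannot, and the Aims sit with the broader group, so these passages must be reconciled. As listed, the data do not identify the Research Question 2a population; that conclusion needs no assumption about effect size, though valve results may exist in the clinical record and simply not be planned for extraction.

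Dilution is a possibility of unknown size. The 71%, 61% and 50% at f = 10%, 20% and 30% rest on an assumed f, on zero gain in already-speaking patients, and on reading 12.22 points as the effect in the intended users. They show only that 61 per group leaves no margin.

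A reader might go further and call a null result uninterpretable. That is too strong. It would still answer the question for the broad population, and voice-related QOL at pre-assessment gives some baseline information on voice. What it could not do reliably, without valve and cuff status, is distinguish lack of effect in the intended users from dilution by others.

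**What to change.** - **Record status.** At pre-assessment, before BLUSA in either group, record speaking-valve success and cuff-deflation tolerance, each yes/no, beside the timings already collected.
- **Use it in the primary comparison.** Specify a between-group, ANCOVA-type comparison of post-assessment QOL-MV, adjusted for baseline QOL-MV and this status. Section 7d names paired t-tests for continuous scores, which offer no place for a covariate. Adjustment alone does not undo dilution of the average effect, so the next step is also needed.
- **Pre-specify the subset.** Report the QOL-MV difference with its confidence interval in patients unable to speak by other means, and state that the subset will be smaller than the 61 per group planned. Use the same definition as the denominator for Research Question 2a.
- **Reconcile the text.** State whether broad entry is intended. If so, say so in section 5 and say which population the 12.22-point target refers to. If not, align section 5 with the rationale.

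**Cost.** One or two yes/no fields, a covariate model in place of the paired t-test alone, and one less precise subset result. Broad entry can stay, so this need not slow accrual; restricting entry might, and that trade-off is for the sponsor to weigh.

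### Section 7d sizes the trial to compare changes but calculates from single-time scores, and it names no test of the between-group hypothesis; the stated 80% power is unsupported for changes

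*Combined protocol and SAP*

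**What the plan says.** Three statements in the combined protocol and SAP bear on the primary analysis.

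- **Hypothesis (section 2, Hypothesis 1a).** "The mean health-related QOL scores of patients who use BLUSA will be significantly higher compared to patients who do not use BLUSA". This is a contrast between groups, on scores. Section 7a lists quality of life as the primary outcome.
- **Sample size (section 7d).** The stated purpose is a comparison of changes: "In order to compare changes in health-related quality of life from pre-assessment to post-assessment, we need 73 participants in each group". This figure "is based on a sample size of 61 individuals in each group to achieve 80% power". The assumed effect is a rise of one fifth in the mean score: a starting mean of 61.16 with SD 21.74, and a target mean of 73.38 with SD 26.09. On the error rate: "We assume a two-tailed test with a significance level of $\alpha = 0.05".
- **Analysis (section 7d).** "Paired t-tests will be used to compare pre and post assessment scores for continuous variables". No other test is named for continuous variables. No SD of change and no pre/post correlation is given.

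Sections 4a(A) and 4a(C) list the quality-of-life survey at both the pre- and the post-assessment. Section 4a(B) has the control group receive BLUSA a week later, after both of its assessments, so controls are unexposed when their post-assessment is taken.

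**The concern.** The plan points to three different analyses of the primary outcome: a between-group comparison of scores (Hypothesis 1a), a comparison of changes (the sample-size sentence), and a within-group pre/post comparison (the named test). They have different variances, and the third answers a different question.

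Two things are at stake. First, a paired test within the BLUSA arm credits the device with any change that would have occurred over the week anyway. The delayed-BLUSA control group exists to remove that, yet 7d names no analysis of quality of life that uses the controls for this purpose. Second, the precision of a change score depends on how strongly the pre and post scores are correlated. A calculation without that correlation cannot support a power claim for changes.

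Patients are not blinded (section 4c) and an interim analysis is planned after 12 months (section 7d). If the primary comparison is not fixed beforehand, the choice among the three remains open once results are visible.

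**Working it through.** **Inputs, all from section 7d.** Difference d = 73.38 − 61.16 = 12.22. Score SDs s1 = 21.74 and s2 = 26.09. Two-sided alpha 0.05, power 80%, equal groups. The 61 is taken as the evaluable number per group; the inflation to 73 for dropout is a separate matter and is not used here.

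**1. Reproducing the plan's figure.** For two independent means:

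n per group = (1.96 + 0.842)² × (s1² + s2²) / d² = 7.85 × (472.63 + 680.69) / 149.33 = 60.6, so 61.

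The root-mean-square SD is √(1153.32 / 2) = 24.01. At 61 per group, power is 80.2% by the normal approximation and 79.6% by noncentral t. No correlation enters. This fits a comparison of scores at one time. Hypothesis 1a gives no time point, but post-assessment is when one group has used BLUSA and the other has not.

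**2. The named paired t-test, within one arm.** The SD of change is √(s1² + s2² − 2r·s1·s2), where r is the pre/post correlation. At r = 0 the number of pairs is again 60.6, so 61. Power with 61 pairs (noncentral t) is 79.0% at r = 0, 87.0% at 0.2, 94.4% at 0.4 and 97.2% at 0.5. Power is adequate, but the test uses one arm only.

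**3. Between-group comparison of changes, 61 per group.** The documents give neither r nor a control-arm post-assessment SD, so both are assumptions and are varied. Three SD models:

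- (a) control 21.74 at both times; BLUSA arm 21.74 before and 26.09 after. Change SDs are 21.74·√(2(1 − r)) in controls and √(s1² + s2² − 2r·s1·s2) in the BLUSA arm, combined as a root mean square.
- (b) 24.01 at every time in both arms. Change SD is 24.01·√(2(1 − r)).
- (c) 21.74 at every time in both arms. Change SD is 21.74·√(2(1 − r)).

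Power (noncentral t, d = 12.22):

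| r | (a) | (b) | (c) |
|---|---|---|---|
| 0 | 54.3% | 50.5% | 58.6% |
| 0.2 | 63.6% | 59.6% | 68.2% |
| 0.4 | 75.8% | 72.1% | 80.3% |
| 0.5 | 82.9% | 79.6% | 86.9% |
| 0.6 | 90.1% | 87.6% | 93.1% |

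Power reaches 80% at r of about 0.46 in (a), 0.50 in (b) and 0.40 in (c).

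**4. ANCOVA of post score on group and pre score, 61 per group.** The residual SD is 24.01·√(1 − r²). Power is 79.6% at r = 0, 80% at 0.1, 81% at 0.2, 86% at 0.4 and 90% at 0.5. Among the between-group analyses that use the pre-assessment score, this one keeps the plan's 61 at about 80% power or better over the whole range.

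**The case against.** The strongest reply is that nothing is wrong with the number. Hypothesis 1a is a comparison of mean scores between groups, and 61 per group gives about 80% power for exactly that. The sample-size phrase about changes may be no more than a loose description of a pretest-posttest design in what section 4a calls a pilot study. The figure also works for the named paired test: 61 pairs give 79% power at correlation 0 and more at any positive correlation. Finally, two administrations of the same questionnaire to the same patient about a week apart may well be correlated above 0.5, in which case even a change-score comparison would have roughly 80% power or more.

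Most of this stands, and it limits the point. A reader might infer that the 80% belongs to no analysis in the plan, that 61 can be obtained only from an independent two-sample formula, or that the trial is underpowered for changes. The documents support none of these. The 80% matches the contrast in Hypothesis 1a; 61 also results for pairs at correlation 0; and quoting change-score power only for correlations up to 0.4 would stop at or just below the break-even.

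The reply does not supply the missing test. Section 7d assigns no analysis to the Hypothesis 1a contrast, and a within-arm paired t-test cannot stand in for it however well powered it is. That gap does not depend on any correlation. ANCOVA is also not the only remedy: a two-sample test of post-assessment scores would match both the hypothesis and the calculation. ANCOVA is preferred because it uses the baseline already collected, and in step 4 power rises with any positive correlation.

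**Conclusion.** The point holds as a mismatch between the hypothesis, the sample-size statement and the named test, with no between-group analysis specified for the primary outcome. Carried out as written, the plan would leave the control group unused for Hypothesis 1a, so this is more than missing detail and needs correcting before outcome data are examined.

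The power consequence is conditional. For a between-group comparison of changes at 61 per group, power is about 50% to 93% over assumed correlations of 0 to 0.6 across the three SD models, with 80% reached at about 0.4 to 0.5. Because the documents give no correlation and no SD of change, the stated 80% is unsupported for changes rather than shown to be missed. For post-assessment scores, the stated 80% is reproduced.

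**What to change.** In section 7d:

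1. Name the primary analysis: ANCOVA of post-assessment QOL-MV on group, adjusted for pre-assessment QOL-MV, two-sided at 0.05.
2. Reword the sample-size sentence to say that 61 evaluable patients per group give about 80% power for a between-group difference of 12.22 points in post-assessment score, with SDs of 21.74 and 26.09, and about that or more after baseline adjustment. Remove the reference to comparing changes.
3. Keep the paired t-tests as descriptive within-group summaries only.

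The cost is a wording change in one section. QOL-MV is already scheduled before and after in both groups, so no new data are needed, and no extra patients on this account.

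### Enrolling 73 per group does not cover the stated 20% drop-out: it is 61 × 1.2 where 61 / 0.8 is needed, and it leaves about 58 evaluable

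*Combined protocol and SAP*

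**What the plan says.** Section 7d, on the statistical plan and sample size, states that "we need 73 participants in each group". It then explains the number: "This allows for a 20% drop out rate and is based on a sample size of 61 individuals in each group". The 61 is intended "to achieve 80% power" for a "clinically meaningful 20% increase in health-related QOL mean score from 61.16" (SD 21.74) to 73.38 (SD 26.09). The test is two-sided at 0.05.

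Section 4f says that a participant who is discharged, or whose clinical condition changes so that the device trial cannot continue, leaves the study. Section 4g adds that a participant whose use of the device ends early because of such a change is not re-enrolled. Section 7e ends data collection for the same two reasons. The document gives no other drop-out rate and no inflation formula.

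**The concern.** A drop-out rate normally means the share of enrolled participants who are lost. To finish with a required number, that number is divided by one minus the rate. Multiplying it by one plus the rate gives too few, and 73 looks like the result of multiplying.

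This is the only sample-size justification in the plan, and it supports the primary outcome, quality of life. A reader would take it that losing 20% of each group (14.6 of 73, about 15 people) still leaves 80% power. The losses are also plausible, because the participants are ventilated hospital patients and the plan itself names clinical change and discharge as reasons for leaving. If the allowance is miscalculated, the stated power is not delivered at the stated drop-out.

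**Working it through.** **Inputs, all from Section 7d:** means 61.16 and 73.38; SDs 21.74 and 26.09; two-sided alpha 0.05; power 80%; 61 evaluable and 73 enrolled per group; drop-out 20%.

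**1. Reproduce the 61.**
- Difference: 73.38 − 61.16 = 12.22, which is 20.0% of 61.16.
- Common SD: √[(21.74² + 26.09²)/2] = 24.01.
- Two independent groups, normal approximation: n = 2 × [24.01 × (1.960 + 0.842) / 12.22]² = 60.62, rounded up to **61**. This matches the plan.
- Variants do not match: SD 21.74 alone gives 50, SD 26.09 alone gives 72, a one-sided test gives 48, and the t-test version gives 62.

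**2. Try to reproduce the 73.**
- Dividing by the retained share: 61 / (1 − 0.20) = 76.25, rounded up to **77**. This does not match.
- Multiplying by one plus the rate: 61 × 1.20 = 73.2, rounded down to **73**. This matches.

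**3. What 73 delivers.**
- With 20% loss: 73 × 0.80 = 58.4, about 58 evaluable per group.
- Largest loss that still leaves 61: (73 − 61)/73 = 12/73 = **16.4%**.
- Check on 77: 77 × 0.80 = 61.6, which meets the requirement.
- Shortfall: 77 − 73 = 4 per group, or 154 − 146 = 8 in total.

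**4. Power for the two-group comparison** (difference 12.22, SDs as above):

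| Evaluable per group | Normal approximation | Welch t-test |
|---|---|---|
| 61 | 80.2% | 79.6% |
| 58 | 78.2% | 77.5% |

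By either method the drop from 61 to 58 costs about 2 percentage points. The Welch column starts slightly below 80% at 61, so its whole gap from 80% should not be put down to drop-out.

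**5. Would baseline adjustment recover the power?** In an analysis of covariance (ANCOVA) on the baseline score, the residual SD is multiplied by √(1 − ρ²), where ρ is the pre-post correlation. With 58 per group (normal approximation), power is 79.9% at ρ = 0.2, 81.9% at ρ = 0.3 and 88.6% at ρ = 0.5. The documents give no value for ρ, so these are assumed values.

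**The case against.** **The 20% could be a margin on completers.** On that reading 73 is right. But the text does not say so, and it is not the usual meaning of a drop-out rate. Sections 4f and 4g describe enrolled participants leaving, so losses come out of the 73.

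**The power loss depends on the test.** The only test Section 7d names for continuous scores is a paired t-test of pre against post. With 58 participants and the same means and SDs, a paired test would have 80.2% power at an assumed pre-post correlation of 0.05 (normal approximation), 81.0% at 0.1 and 89.4% at 0.3 (both t-test). That is a fair limit on the consequence. It does not rescue the 73, because the enrolment error is the same whatever the test. Nor does it fit the plan's own basis. The 61 is stated for each group and matches the two-group formula, and Hypothesis 1a compares users with non-users. A paired formula gives 61 only at zero correlation, where the variance of the change, 21.74² + 26.09², equals 2 × 24.01², and power at 58 is again 78.2%. The mismatch between the two-group sample size and the paired test is a separate matter.

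**It is a small effect in a study labelled a pilot, with a round, unsourced drop-out rate.** This stands. Two points of power would not change the trial's value. But the plan chose to state 80% power after 20% loss, so the statement should be correct.

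**Conclusion.** The point holds. By the plan's own inputs, 73 per group does not give 80% power after 20% drop-out. It leaves about 58 evaluable per group and about 78% power, or it keeps 61 evaluable if the loss is no more than 16.4%. The shortfall is 4 per group, 8 in total, and about 2 percentage points of power.

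The enrolment arithmetic assumes only that the 20% is a share of those enrolled and that those who leave are not evaluable. The power figures also assume an independent-group comparison with the stated means and SDs. The error is certain and its consequence modest. It should be corrected, but it does not put the design in doubt.

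**What to change.** Amend the sample-size sentence in Section 7d in one of three ways:

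- Keep 73 per group and 20% drop-out, and state that about 58 per group will be evaluable, with about 78% power.
- Keep 73 per group and 80% power, and state that the allowance covers about 16% drop-out.
- Keep both 20% drop-out and 80% power, and raise enrolment to 77 per group (154 in total, against 146).

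The first two cost one sentence and a slightly less favourable claim. The third costs 8 more participants.

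Optionally, if the between-group analysis is specified as ANCOVA on the baseline score of the quality-of-life questionnaire for ventilated patients (QOL-MV), the plan may state the power for 58 per group under a justified pre-post correlation. It would need to say that the correlation is assumed: about 82% at 0.3 and 89% at 0.5, but still just under 80% at 0.2. The correction above does not depend on this.
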